Protocol

1. Project Title:

Resveratrol and Exercise to Treat Functional Limitations in Late Life (RESTORES)

2. Investigators:

[name]

[name]

[name]

[name]

[name]

[name]

3. Abstract:

With persons aged ≥ 65 years representing the fastest growing segment of the U.S. population, the prevention of age-related functional decline and disability is an important public health priority. The loss of functional abilities in advanced age is associated with not only the onset of disability and the loss of independence but also with increased rates of morbidity and mortality. To date, physical exercise is the only intervention consistently demonstrated to improve physical function among older adults and is increasingly being considered the standard of care for treating functional limitations. However, significant variability exists in responsiveness to exercise. As such, many individuals do not achieve clinically-significant improvements in function despite good adherence. Accordingly, there is a need to identify adjuvant therapies capable of improving the efficacy of exercise in treating older adults with functional impairments. This project is a pilot study to investigate the potential of resveratrol, a commercially-available nutritional product, to enhance the efficacy of physical exercise in improving physical function among older adults with functional limitations. The overarching objective of this project is to evaluate the safety and efficacy of an intervention combining resveratrol supplementation and physical exercise among sedentary persons aged 65 years objectively-measured functional limitations. A total of 60 participants will be recruited to participate in this three month intervention study. All participants will engage in a center-based exercise program 2/days per week and will be randomly assigned to consume 1) placebo, 2) 500 mg/day resveratrol, or 3) 1000 mg/day resveratrol. This study will provide critical information regarding the influence of the combination of resveratrol and exercise (REX) on objectively-measured and self-assessed indices of physical function. The study will also provide biologic information regarding the relative effects of REX on skeletal muscle mitochondrial function.

4. Background:

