2. To determine the variance of secondary outcomes and short-term effects of the intervention on these outcomes, including: (1) exercise capacity, evaluated by distance walked during the 6-minute walk test, (2) lower-extremity function, assessed by the Short Physical Performance Battery (SPPB), (3) skeletal muscle strength and endurance, assessed by isokinetic muscle testing, and 4) self-assessed functional limitations, evaluated by the Late-Life Disability Questionnaire.
3. To (a) assess the effects of resveratrol on exercise-induced changes in key indices of skeletal muscle mitochondrial function and quantity, and (b) determine the extent of association between changes in these mitochondrial outcomes and changes in measures of physical function.

6. Research Plan:

We propose to conduct a randomized, controlled pilot trial to test that resveratrol improves functional responses of physically-limited older adults to chronic exercise training. Following study entry, participants (N = 60) will be randomly assigned to either EX or one of two REX groups for 12 weeks. Each condition will consist of two center-based resistance training sessions per week.

6.1 Participants: Eligible participants will be males or females ≥ 65 years of age with a sedentary lifestyle and objectively-measured functional limitations.

Table 6.1. Inclusion and exclusion criteria

Inclusion Criteria

• Age 65 years• > 290 seconds needed to complete long-distance corridor walk test, as an indicator of functional limitation and moderate to low aerobic fitness³• Sedentary lifestyle, defined as <150 min/wk of moderate physical activity as assessed by CHAMPS questionnaire²¹• Willingness to be randomized to either treatment group• Willingness to participate in all study procedures
Exclusion criteria

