6.3 Screening and Study Entry: Interested individuals will initially complete a pre-screening interview by phone. Participants deemed eligible based on the pre-screening invited to an in-person screening visit. During this visit, potential participants will first be asked to give their informed consent and then will be screened for study entry criteria. Initial screening procedures will include a review of their medical history, physical activity habits, medication use, cognitive function (assessed by the Mini Mental State Exam), and a physical exam performed by a study physician. The study physician will review collected information relevant to potential participant's health and make recommendation on this individual's participation in this trial.

Participants will then be asked to complete the long-distance corridor walk test to evaluate functional status and aerobic fitness. If all study entry criteria are met, participants will be scheduled to return to the clinic for baseline assessments. In addition, the study participants will be asked to sign Medical Records Release Authorization. This Authorization will be used exclusively to obtain medical records to acquire facts, details, and outcomes of Serious Adverse Events that occurred during the study and have to be reported to the sponsor and/or IRB.

6.4 Baseline Assessment and Randomization: If all study entry criteria are met, participants will be scheduled to return to the clinic for baseline assessments prior to randomization. During this visit, participants will be asked to complete validated study questionnaires, including the Late-Life Disability Instrument²⁴ and provide a fasting blood sample for evaluation of clinical safety lab values. Participants will also complete the Short Physical Performance Battery (SPPB), a 6-minute walk test, and assessments of muscle strength. Finally, the study coordinator will provide participants with an armband physical activity monitor and dietary intake form to take home to objectively evaluate baseline physical activity and dietary habits. Staff members will then discuss randomization procedures with participants. Participants who agree to participate in the muscle biopsy procedure will be scheduled for a separate visit prior to initiation of study interventions.

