Measurement of skeletal muscle (1) *in situ* mitochondrial respiration, (2) proliferative activated receptor-γ coactivator 1α (PGC-1α), (3) mitochondrial DNA, (4) citrate synthase (CS) activity, and (5) cytochrome C oxidase (COX) activity will be completed the *OAIC Metabolism and Translational Science Core*, led by co-investigator [name]. Mitochondrial respiration will be determined immediately on freshly saponin-permeabilized muscle fibers as published previously⁸ using the high-resolution Oxygraph-2k (Oroboros, Innsbruck, Austria). Skeletal muscle PGC-1α, mitochondrial DNA content, as well as CS and COX activities will be determined using well-standardized, validated methods with excellent test re-test reliability in the Core laboratory.⁴²

6.10 Sample size justification. This study will help generate precise estimates of effect variance in the population in which a subsequent larger-scale study will be conducted. Published recommendations for the design of pilot studies indicate that a sample of 15-20 participants per randomized arm is typically sufficient to estimate a parameter for a future trial.⁴³⁻⁴⁵ The enrollment sample of 60 participants is intended to provide preliminary data necessary to indicate feasibility of a larger trial and to provide descriptive estimates of effects. It will also provide for nominal estimation (using a 95% CI) of mean changes in dependent variables within each arm. While it is possible that statistically significant differences between arms may be observed, this pilot trial is not intended to be powered to observe such differences with high probability. For aims 1 and 2, assuming $\alpha = 0.05$, we will have 80% power to detect an effect size of 0.74 for outcomes with three assessments (walking speed, muscle function, exercise capacity) and 0.79 for outcomes with two assessments (SPPB, self-assessed function, mitochondrial measurements), assuming a repeated measures correlation of 0.5. For the primary outcome of walking speed, we expect this detectable difference to be 0.12 m/sec based on a SD of 0.16 m/sec observed in the LIFE studies. For secondary aims, the following detectable effects sizes are expected based on our prior experience in LIFE and LIFE-P: SPPB, 1.3 points; 6-minute walk distance, 22.2 m; isokinetic peak torque, 27.8 Nm; and Late Life Disability Instrument Score; 3.8 points.

[figure not shown]

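### The three-arm allocation has no stated ratio or blocking and takes no account of the optional biopsy subset that alone supplies the Aim 3 data: a modest precision loss that is cheap to avoid

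*Combined protocol and SAP*

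**What the plan says.** - **Allocation.** The abstract says that participants "will be randomly assigned to consume 1) placebo, 2) 500 mg/day resveratrol, or 3) 1000 mg/day resveratrol". Section 6 says that "participants (N = 60) will be randomly assigned to either EX or one of two REX groups for 12 weeks". No section gives an allocation ratio, a block scheme or a stratification factor.
- **Biopsy.** Section 5 makes the biopsy optional, at baseline and at 12 weeks. Table 6.1 adds exclusions that apply to the biopsy alone (prescription anti-platelet or anti-coagulant drugs, conditions that impair wound healing, lidocaine allergy). Aim 3 rests on these samples. No expected number is given.
- **Timing.** Section 6.4 states: "Participants who agree to participate in the muscle biopsy procedure will be scheduled for a separate visit prior to initiation of study interventions". It does not say whether agreement to the biopsy, or the biopsy itself, comes before randomisation.
- **Sample size.** Section 6.10 cites guidance that "a sample of 15-20 participants per randomized arm is typically sufficient to estimate a parameter for a future trial". It then states "we will have 80% power to detect an effect size of 0.74 for outcomes with three assessments" and "0.79 for outcomes with two assessments (SPPB, self-assessed function, mitochondrial measurements", at alpha 0.05 with a repeated-measures correlation of 0.5. That sentence is introduced as covering Aims 1 and 2, yet it lists the Aim 3 measurements. The same section says that the pilot is not meant to have high power for differences between arms.

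**The concern.** The biopsied participants are a smaller group, selected by willingness and by medication and health criteria, and they answer Aim 3 alone. Even if the whole trial came out at exactly 20 per arm, the biopsied participants could fall unevenly over the three arms. An uneven split widens the dose-versus-placebo intervals for the mitochondrial outcomes and brings nothing in return. It also weakens the within-arm 95% intervals that Section 6.10 promises, for whichever arm comes out small.

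A second and separate gap concerns the whole trial. With no ratio or blocking written down, the 15 to 20 per arm that Section 6.10 relies on is not assured. Neither gap can be repaired at the analysis stage.

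**Working it through.** **1. The plan's own figures.** Inputs from Section 6.10: alpha 0.05 (taken as two-sided), power 80%, correlation 0.5. Assumed: 20 per arm, from 60/3. Formula: detectable effect = δ × √[(1 + (m − 1) × 0.5)/m], where m is the number of assessments and δ is the standardised difference that a two-sample t-test detects with 80% power.
- At 20 v 20, δ = 0.909.
- m = 3: 0.909 × 0.8165 = 0.742 (plan: 0.74).
- m = 2: 0.909 × 0.8660 = 0.787 (plan: 0.79).
- 0.74 × 0.16 = 0.118 m/sec (plan: 0.12).

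The figures therefore fit 20 v 20. A 15 v 30 comparison fits as well (0.740 and 0.785), so they do not establish the ratio.

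**2. Whole trial.** In 400,000 simulated unrestricted 1:1:1 allocations of 60, some arm falls below 15 in about 19%. An exact 20/20/20 split occurs in about 1%.

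**3. Biopsy subset.** Assumption: 30 biopsied, so 10 per arm if even. Two cases: unrestricted allocation (multinomial), and arms fixed at 20/20/20 without regard to biopsy (hypergeometric).

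Variance ratio for a contrast = (1/n_placebo + 1/n_dose) / (2/10). Examples: 7 v 13 gives (0.1429 + 0.0769)/0.2 = 1.10; 7 v 10 gives (0.1429 + 0.1000)/0.2 = 1.21.

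| 30 biopsied | Unrestricted | Blocked overall only |
|---|---|---|
| An arm of 7 or fewer | 48% | 25% |
| Mean variance rise, a given dose v placebo | 8% | 4% |
| Mean standard error rise, same contrast | 3.6% | 1.7% |
| Mean variance rise, worse of the two contrasts | 19% | 11% |
| 90th percentile, worse contrast | 42% | 22% |

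For 20 to 40 biopsied, the mean variance rise of the worse contrast is 28% down to 14% unrestricted, and 19% down to 6% if blocked overall.

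**4. Power.** Same t formula, m = 2, effect 0.79. With 30 biopsied and an even split, power is 48.8%. Averaged over chance splits it is 47.9% (arms fixed at 20) or 46.5% (unrestricted). For 18 to 48 biopsied the mean loss is at most about 2.5 points.

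**5. Imbalance against subset size.**

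| Biopsied arms | Detectable effect | Power at 0.79 |
|---|---|---|
| 20 v 20 | 0.79 | 80% |
| 16 v 16 | 0.89 | 70% |
| 12 v 12 | 1.04 | 57% |
| 10 v 10 | 1.15 | 49% |
| 7 v 13 | 1.20 | 45% |
| 8 v 8 | 1.31 | 40% |

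Moving from 10 v 10 to 7 v 13 costs 0.05 in detectable effect. Moving from 20 to 10 per arm costs 0.36.

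**6. Within-arm interval.** Half-width in SD units = t(0.975, n − 1)/√n. For n = 10: 2.262/3.162 = 0.72. For n = 7: 2.447/2.646 = 0.92, which is wider by a factor of 0.92/0.72 = 1.28.

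**The case against.** The strongest reply is that this is a 60-person pilot, that Aim 3 is not the primary aim, and that Section 6.10 disclaims high power for between-arm differences. The mean loss in standard error is a few per cent, and the larger figures describe the worse of two contrasts on the variance scale. The documents are silent on method, so unrestricted allocation is itself an assumption; the sponsor may well intend blocks. Aim 3(b), on association of changes, does not need balanced arms. All of this stands, and it sets the severity. It does not remove the point: Section 6.10 still promises within-arm intervals, and the improvement costs little.

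A reader might infer more in three ways that the documents do not support.
- **That stratifying would secure 20 per arm for Aim 3.** It would not. Section 6.10 never states 20 per arm, and the biopsy subset is smaller because the procedure is optional and has its own exclusions. Stratification changes the split of the subset, not its size.
- **That an uneven split would tilt adverse-event ascertainment.** Section 6.11 places the extra calls in the days after the biopsy. The baseline biopsy precedes the interventions and the other is at the 12-week close-out, so the calls fall largely outside treatment. All participants are asked to report events at scheduled data-collection times.
- **That chance imbalance in biopsy status would bias gait speed or the other Aim 1 and 2 outcomes.** No section links biopsy status to those outcomes, and chance imbalance in a covariate is imprecision, not bias.

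**Conclusion.** The point holds as a low-severity design improvement. Nothing in Sections 6 or 6.4 balances the arms within the subset that supplies Aim 3. At an assumed 30 biopsied, an arm of 7 or fewer arises in 48% of trials (unrestricted) or 25% (blocked overall), for an average variance rise of about 8% or 4% in a given contrast and at most about 2.5 points of power. Separately, the 15-per-arm floor would be missed in about 19% of trials if allocation were unrestricted.

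These sizes rest on the assumed biopsy number, on 1:1:1 allocation, and on biopsy participation being unrelated to arm. The larger threat to Aim 3 is the size of the subset: 0.79 is reproduced for mitochondrial measurements only if comparisons have about the precision of 20 v 20, which an optional biopsy does not provide unless nearly everyone takes part.

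**What to change.** 1. In Section 6, state 1:1:1 randomisation in permuted blocks, stratified by biopsy participation (yes or no).
2. In Section 6.4, require biopsy agreement and eligibility to be recorded before randomisation. Preferably, randomise after the baseline biopsy has been obtained or declined, so that membership of the subset is fixed before the arm is assigned.
3. Keep the stratum as a factor in the between-arm analyses. It matters for the whole-trial outcomes; within the biopsied subset it is constant.
4. In Section 6.10, state the expected number of biopsied participants and restate the 0.79 for mitochondrial measurements to match, for example about 1.15 at 10 per arm or 1.04 at 12 per arm. Allow for missing week-12 biopsies, which stratifying at baseline cannot prevent.
5. Reconcile the Table 6.1 criterion on willingness to undergo every study procedure with the optional status of the biopsy.

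Cost: a stratified list in place of a single one, a few incomplete blocks, and a short delay to randomisation for biopsy participants. Items 4 and 5 are edits to the text only.

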6.6 Adherence to interventions. To enhance adherence to the study interventions (compliance), we will utilize empirically-supported techniques which we have successfully utilized in prior studies. Our first step will be to fully inform participants of study requirements before randomization and enroll only those persons who are willing to complete all study procedures. Undoubtedly, however, issues arise after randomization with the potential to limit compliance. Common causes of poor compliance include vacations, spouse care, fatigue, and fluctuations in motivation, perceived lack of benefit, physical discomfort, and adverse health experiences. First, we have designed the trial, including the inclusion/exclusion criteria and physician monitoring, to limit the likelihood of experiencing adverse health events in response to the interventions. In addition, care will be taken by the interventionists to promote the safe engagement in the exercise intervention. For other issues of non-compliance, we will approach this potential problem using a social problem solving model ("toolbox") approach in dealing with individual adherence problems.²⁸ This approach assumes that the process of changing behavior is a collaborative effort between the participant and the interventionists, and that behavior change can be readily undertaken during the regular weekly contacts that intervention staff will initiate throughout the course of the intervention, as well as during face-to-face visits. Our team has successfully applied this type of problem-solving approach in promoting adherence to behavioral interventions in prior studies.

6.7 Follow-up and Close-out visits. In addition to baseline and screening visits, assessment visits will be conducted at 6 weeks (follow-up) and 12 weeks post-randomization. During the 6-week assessment visit, the research team will evaluate participant vital signs, collect blood samples, inquire about any adverse experiences since the last visit, and perform tests of physical performance evaluated performed at baseline. During the close-out (12 week) visit, the team will perform the same evaluations as during the 6-week visit, as well as administer study questionnaires, perform the SPPB, and collect home-based physical activity and dietary information from participants. Skeletal muscle biopsies will also be collected at 12 weeks from willing participants.

6.8. Primary and Secondary Outcome Measures.

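### The 80% power at effect sizes 0.74 and 0.79 in section 6.10 counts all 60 enrolled as analysed, and for the optional-biopsy outcomes 0.79 is not supportable without full participation

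*Combined protocol and SAP*

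**What the plan says.** The abstract describes three arms: participants "will be randomly assigned to consume 1) placebo, 2) 500 mg/day resveratrol, or 3) 1000 mg/day resveratrol". Section 6.10 presents 60 as an enrolment figure: "The enrollment sample of 60 participants is intended to provide preliminary data". It supports that number with a published benchmark of 15 to 20 per arm for estimating a parameter, and says the pilot is not meant to have high power for differences between arms.

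The same paragraph then makes a definite power statement at alpha 0.05: "we will have 80% power to detect an effect size of 0.74 for outcomes with three assessments", and "0.79 for outcomes with two assessments (SPPB, self-assessed function, mitochondrial measurements" (the list ends there), "assuming a repeated measures correlation of 0.5". From an SD of 0.16 m/s it derives a detectable walking-speed difference of 0.12 m/s, and it lists detectable effects for four secondary outcomes.

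The protocol gives no attrition rate, number evaluable, missing-data method, analysis model or named contrast. Section 5 makes the muscle biopsy optional. Table 6.1 adds exclusions for biopsy alone: prescription anti-platelet or anti-coagulant use, poor wound healing and lidocaine allergy.

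**The concern.** A detectable effect should be quoted at the number of participants who will contribute data. If 0.74 and 0.79 need every enrolled participant, they are best-case values presented without that condition, and the reader cannot tell how far they move under ordinary loss.

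For the mitochondrial outcomes, full participation is not even the design. The protocol lets participants decline biopsy and bars some from it, yet it lists these measurements under the same 0.79 as SPPB and self-assessed function. A null mitochondrial result could then be read as ruling out effects that the biopsy subset had little chance of detecting.

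**Working it through.** **Inputs.** From section 6.10: alpha 0.05, power 80%, repeated-measures correlation ρ = 0.5, SD 0.16 m/s, and m = 3 or m = 2 assessments. From the abstract and section 6.10: 60 enrolled in three arms. Assumptions: equal allocation (60/3 = 20 per arm), since no ratio is stated; a two-sided test, since sidedness is not stated; and all loss rates.

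**Formula.** The variance factor for the mean of m correlated measures is f = (1 + (m − 1)ρ)/m.
- m = 3: f = (1 + 2 × 0.5)/3 = 0.667, √f = 0.8165
- m = 2: f = (1 + 0.5)/2 = 0.75, √f = 0.866

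Power comes from the noncentral t distribution with 2n − 2 degrees of freedom and noncentrality (d/√f) × √(n/2), where n is the number analysed per arm.

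**Reproducing the plan's figures.** At n = 20 (38 degrees of freedom), a single measure has 80% power at 0.909 SD.
- Three assessments: 0.909 × 0.8165 = 0.742 (stated 0.74)
- Two assessments: 0.909 × 0.866 = 0.787 (stated 0.79)
- Walking speed: 0.742 × 0.16 = 0.119 m/s (stated 0.12)

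Power is 79.8% at 0.74 and 80.3% at 0.79, so there is no reserve.

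**Other bases tried** (three / two assessments):
- One-sided t, 20 v 20: 0.65 / 0.69
- Change scores, 20 v 20: 0.79 / 0.91
- ANCOVA on the mean of post-baseline values, 20 v 20: 0.64 / 0.79
- Placebo v pooled resveratrol, 20 v 40: 0.64 / 0.68
- Placebo v pooled resveratrol, 15 v 30: 0.740 / 0.785 (0.7849 before rounding, so 0.78 to two decimals)

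Of the bases tried, only the two-sided pairwise t test at 20 v 20 gives both stated figures to two decimals.

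**Effect of loss.** Loss is taken as equal across arms, and anyone lost is dropped altogether.

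| Assumed loss | n per arm | Detectable effect, 3 / 2 assessments | Walking speed (m/s) | Power at 0.74 / 0.79 |
|---|---|---|---|---|
| 0% | 20 | 0.742 / 0.787 | 0.119 | 79.8% / 80.3% |
| 5% | 19 | 0.76 / 0.81 | 0.122 | 77.6% / 78.1% |
| 10% | 18 | 0.785 / 0.83 | 0.126 | 75.2% / 75.8% |
| 20% | 16 | 0.84 / 0.89 | 0.134 | 69.9% / 70.4% |
| 25% | 15 | 0.865 / 0.92 | 0.138 | 66.9% / 67.4% |

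**Biopsy subset (two assessments).** The protocol does not say how many will give both samples, so these sizes are illustrations.
- 12 per arm (36 in all): 1.197 × 0.866 = 1.04; power at 0.79 is 57%
- 10 per arm (30 in all): 1.325 × 0.866 = 1.15; power at 0.79 is 49%

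**The case against.** **The pilot disclaims power.** This is true, and it stands as a limit on the weight of the point. The sample size rests on the benchmark of 15 to 20 per arm, and with 20 per arm a 25% loss still leaves 15. Aim 1 is to obtain data for sizing a later trial, and no decision depends on the 80%. But the disclaimer does not tell the reader that the figures quoted next to it assume complete data.

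**No dropout is documented.** A reader might infer from section 6.6 ("Undoubtedly, however, issues arise after randomization with the potential to limit compliance") that the protocol itself predicts loss of data. It does not: that section concerns adherence to the interventions, and someone who misses sessions can still attend the 12-week assessment. Section 6.11 allows the study physician to withdraw a participant over abnormal laboratory values, so loss is possible, but its rate is unknown.

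**Dropping people entirely is the worst case.** For three-assessment outcomes, a repeated-measures model could use the baseline and 6-week values of someone lost later. That stands as a possibility, although no model is specified. Two-assessment outcomes have no 6-week value to use.

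**The contrast is inferred.** If the intended contrast were placebo against pooled resveratrol, 15 v 30 would have 80.0% power at 0.74 and 80.5% at 0.79, so a 25% loss would already be absorbed. That reading misses the stated 0.79 on rounding, and the protocol mentions neither pooling nor a 25% loss, but it cannot be excluded outright.

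**The shift is small at low loss.** At 5% loss the walking-speed figure still rounds to 0.12 m/s. This is correct.

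**Conclusion.** The point holds, with modest weight for most outcomes. The figures in section 6.10 correspond to 20 v 20 with all 60 enrolled analysed, and this condition is not stated. On the pairwise reading, with equal allocation and complete-case loss, power falls by about 2 points at 5% loss, 5 at 10% and 10 at 20%. The detectable walking-speed difference rises by about 0.015 m/s at 20% (0.134 − 0.119).

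For the mitochondrial outcomes the point is firmer, because optional participation and separate exclusions are written into the design. The 0.79 is not supportable there unless all 60 are biopsy-eligible, consent and give both samples.

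Three stronger readings are not supported:
- A reader might infer an arithmetic error. There is none; the stated figures reproduce.
- A reader might infer that the trial is too small. Its size rests on estimation, and the benchmark tolerates a 25% loss.
- A reader might infer that every secondary detectable effect has been shown to be too favourable in its own units. Section 6.10 does not give the secondary SDs, so those values cannot be checked from the documents.

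**What to change.** Keep N = 60. In section 6.10:

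1. Name the contrast (pairwise, one resveratrol arm against placebo, as the figures imply), the allocation ratio and the sidedness of alpha.
2. State the 12-week retention expected from the team's prior studies, and restate the detectable effects at the resulting number analysed per arm. At 20% loss, for example, these would be 0.84 and 0.89, with 0.134 m/s for walking speed. Restate the secondary effects from their own SDs.
3. Take the mitochondrial outcomes out of the 0.79 group and give them a separate, larger detectable effect at the expected number of paired biopsies per arm.

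If no retention figure is available, the least that is needed is to label the present figures as conditional on all 60 completing and, for the mitochondrial outcomes, on all 60 giving both biopsies.

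The cost is a few lines of text and slightly less favourable stated figures. No participants are added and the design does not change.

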Subsequent studies using animal models of aging have reported that improvements in physical performance are greater in response to the combination of exercise and resveratrol than from either treatment alone.¹⁵⁻¹⁸ These studies overwhelmingly suggest that improvements in performance likely manifest as a result of enhanced skeletal muscle mitochondrial function. Thus, resveratrol appears to specifically target a key physiologic mechanism through which exercise improves physical function among older adults. We hypothesize that enhancing mitochondrial function may enhance physiologic adaptations to exercise such as aerobic fitness and skeletal muscle endurance. However, despite the promising findings from pre-clinical models, experimental data are sparse regarding the effects of this combined approach in humans. Consequently, well-controlled studies are needed to determine if the benefits of combining resveratrol with exercise demonstrated in pre-clinical studies can be translated to humans. *Therefore, the purpose here, as the next step in pursuit of our long-term goal, is to evaluate the relative efficacy of combining physical exercise with oral resveratrol supplementation for improving the physical function of older adults at risk for disability.*

5. Specific Aims:

The objective of this study is to conduct a pilot study to refine and finalize elements critical to conducting a future, definitive randomized, controlled trial (RCT). We propose to recruit 60 persons aged \geq 65 years with functional limitations and follow them for 12 weeks. Participants will be randomly assigned to receive either (1) placebo plus 2 days/week of supervised, center-based, multi-modal exercise (EX), or (2) the same exercise program combined with either 500 or 1000 mg/day of resveratrol (REX). We will also collect skeletal muscle biopsies at baseline and 12 weeks from willing participants (i.e. optional for study participation) to evaluate skeletal muscle mitochondrial adaptations to the interventions. This study will enable us to address the following aims, all of which are of critical importance for designing a full-scale trial.

1. To obtain critical data necessary to project the sample size needed for a full-scale trial using the change in 4m usual gait speed, a key predictor of health and survival in older adults,^{2,19,20} as the primary outcome.

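### Section 6.10 gives the optional-biopsy mitochondrial outcomes the same 0.79 SD detectable effect as full-sample outcomes, and its 0.74 SD (0.12 m/sec) for walking speed is tied to no named comparison

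*Combined protocol and SAP*

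**What the plan says.** The trial has three arms; participants "will be randomly assigned to consume 1) placebo, 2) 500 mg/day resveratrol, or 3) 1000 mg/day resveratrol" (Section 3). The enrolment target is 60.

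Section 6.10 takes alpha 0.05 and states "80% power to detect an effect size of 0.74 for outcomes with three assessments (walking speed, muscle function, exercise capacity"). A second figure, for measures taken only at the start and the end, follows in the same sentence: "0.79 for outcomes with two assessments (SPPB, self-assessed function, mitochondrial measurements), assuming a repeated measures correlation of 0.5". For walking speed it adds: "we expect this detectable difference to be 0.12 m/sec based on a SD of 0.16 m/sec observed in the LIFE studies". It does not give the arms compared, the time point or summary, the model, the sidedness of the test, the allocation ratio or the expected loss.

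The same section bases the sample size on published advice that "a sample of 15-20 participants per randomized arm is typically sufficient to estimate a parameter for a future trial", and cautions that "this pilot trial is not intended to be powered to observe such differences with high probability".

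Aim 1 (Section 5) is to "project the sample size needed for a full-scale trial using the change in 4m usual gait speed". Section 5 also provides for "skeletal muscle biopsies at baseline and 12 weeks from willing participants (i.e. optional for study participation"). Section 6.7 again limits the week-12 biopsy to willing participants, and Table 6.1 has a separate list of exclusions for biopsy only, including anti-platelet and anti-coagulant prescriptions. Baseline is measured before randomisation (Section 6.4); the only later assessment visits are at weeks 6 and 12 (Section 6.7).

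**The concern.** There are two problems, and the first is the firmer.

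**Mitochondrial outcomes.** One detectable effect is printed for outcomes measured on everybody and for outcomes measured on a self-selected and further restricted subset. If the figure needs the full arm size, the subset cannot share it. Aim 3 rests on these measurements.

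**Walking speed.** Only two visits follow randomisation, so an outcome with three assessments must be counting the pre-randomisation baseline. Baseline carries no treatment effect. A reader therefore cannot tell what difference the 0.74 SD refers to, or set it beside the change in gait speed named in Aim 1. This is the plan's only statement of what the pilot can detect on its primary outcome, and the pilot exists to plan a larger trial.

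**Working it through.** **Inputs from Section 6.10:** alpha 0.05, power 80%, correlation 0.5, walking-speed SD 0.16 m/sec, N = 60.

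**Assumptions, because the plan is silent:** equal allocation (60/3 = 20 per arm), one dose versus placebo, two-sided t test, no loss, equal correlation between all visits, and 0.16 taken as the SD at a single visit.

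**Step 1. Reproduce the printed figures.** The noncentral t for 20 vs 20 (38 df) gives a single-visit detectable difference of 0.909 SD. Multiply by the square root of a variance factor. For the mean of k visits the factor is (1 + (k − 1) × 0.5)/k.

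- k = 3: factor 2/3, 0.909 × √(2/3) = 0.742 SD, and 0.742 × 0.16 = 0.119 m/sec. Printed: 0.74 and 0.12.
- k = 2: factor 3/4, 0.909 × √0.75 = 0.787 SD. Printed: 0.79.

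For two visits, baseline-adjusted week 12 has the same factor, 1 − 0.5² = 0.75, so 0.79 is a proper figure if the analysis adjusts for baseline. On change scores the factor is 2(1 − 0.5) = 1 and the figure is 0.91 SD.

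**Step 2. Mitochondrial outcomes.** Keep factor 0.75 and vary the number biopsied per arm. The 15 and 10 are assumptions; the plan gives no expected number.

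| Per arm | Single-visit d | Detectable, baseline-adjusted | Power at 0.79 SD |
|---|---|---|---|
| 20 | 0.909 | 0.79 SD | 80% |
| 15 | 1.060 | 0.92 SD | 67% |
| 10 | 1.325 | 1.15 SD | 49% |

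**Step 3. Walking speed at 20 vs 20 under contrasts that do not count baseline as an outcome.**

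| Contrast | Variance factor | Detectable | Power at 0.74 SD |
|---|---|---|---|
| Baseline-adjusted week 12 | 0.75 | 0.79 SD = 0.126 m/sec | 75% |
| Change to week 12 | 1 | 0.91 SD = 0.145 m/sec | 63% |
| Baseline-adjusted mean of weeks 6 and 12 | 0.75 − 0.25 = 0.5 | 0.64 SD = 0.103 m/sec | 90% |

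None of these is 0.74, and they lie on both sides of it.

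**Step 4. Other routes to the factor 2/3.**

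- A longitudinal model with baseline means constrained equal, and a week-6 effect equal to a times the week-12 effect, has information 1.5a² − a + 1.5. At a = 2/3 this is 1.5, so the factor is again 2/3 and the figure 0.742 SD. With two visits the same model gives 0.787 SD.
- Adjusting week 12 for both baseline and week 6 also gives 1 − 2 × 0.25/1.5 = 2/3.

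**Step 5. Other sample splits.**

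- 30 vs 30 gives 0.74 SD on change scores, but the same value for two-assessment outcomes, so it misses the printed 0.79.
- Pooled doses versus placebo (40 vs 20) gives 0.68 SD for baseline-adjusted week 12 and 0.78 SD for change.
- A one-sided normal approximation with 15 per arm also matches the pair: (1.645 + 0.842) × √(2/15) = 0.908, giving 0.741 and 0.786 SD. The plan states neither one-sided testing nor the loss this would imply.

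**The case against.** **The walking-speed figure is not shown to be wrong.** A reader might infer from the three-visit average that 6.10 used an invalid contrast, or that the pilot is underpowered for gait speed. The documents support neither. No contrast is named, so none can be shown to be the wrong one. The constrained-baseline model in Step 4 is a legitimate randomised comparison and yields both printed figures, although it needs an effect shape that the plan never states. And 0.12 m/sec is conservative for the baseline-adjusted mean of weeks 6 and 12: at 15 per arm that contrast still detects 0.749 × 0.16 = 0.120 m/sec. This objection stands. What remains is that the figure cannot be interpreted as printed.

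**The mitochondrial shortfall depends on the comparison.** If both doses were pooled, 15 biopsied per arm means 30 vs 15, and 1/30 + 1/15 = 1/20 + 1/20, so about 0.79 SD would still be detectable (0.785 by noncentral t). At 20 vs 10 it would be 0.97 SD. With one-sided testing, power at 0.79 SD for 15 per arm is 79%. This is fair, but under either reading the full-sample outcomes would have a smaller detectable effect than the biopsy outcomes, so one shared figure would still not fit. The numbers biopsied are also assumed; only the direction, fewer than 20 per arm, is to be expected from the plan.

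**No decision rests on these figures.** The sample size comes from a rule for pilots, and 6.10 disclaims power for arm differences. This also stands, and it keeps the point minor.

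**Conclusion.** The point holds at minor weight.

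- **Mitochondrial outcomes:** printing 0.79 SD for a voluntary, further restricted subset as well as for the full sample is an error whichever comparison was meant. For one dose versus placebo, two-sided, at an assumed 15 to 10 biopsied per arm, the detectable effect is 0.92 to 1.15 SD, with 67% to 49% power at 0.79 SD.
- **Walking speed:** 0.74 SD is most simply reproduced by averaging three visits including baseline, but not uniquely. Standard contrasts at 20 vs 20 run from 0.103 to 0.145 m/sec, with 90% down to 63% power at 0.74 SD. Whether 0.12 m/sec is too favourable cannot be decided until 6.10 says what is being compared.

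All figures assume equal allocation, correlation 0.5 and no loss.

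**What to change.** In Section 6.10:

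1. Take the mitochondrial measurements out of the 0.79 figure. State the expected number biopsied per arm and the matching detectable effect (0.92 SD at 15 and 1.15 SD at 10, baseline-adjusted, one dose versus placebo).
2. For walking speed, muscle function and exercise capacity, replace 0.74 with the figure for a named comparison: arms, time point or summary, baseline adjustment and sidedness. Do not count baseline as an outcome visit. For example: each dose versus placebo, 20 vs 20, two-sided alpha 0.05, correlation 0.5, baseline-adjusted week 12, 80% power at 0.79 SD = 0.13 m/sec. If another contrast is intended, give its own figure.
3. Bring the printed 6-minute walk and peak torque differences into line with the same contrast, using their own SDs, which 6.10 does not print.
4. Say that 0.79 for SPPB and self-assessed function presumes baseline adjustment; on change scores it is 0.91 SD.

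The cost is a few sentences and a commitment to a named contrast. The mitochondrial figure becomes clearly less favourable for a single-dose comparison. The walking-speed figure moves slightly, in a direction set by the contrast chosen. Sample size, visits and procedures do not change.
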